Due to slow and low recruitment and following discussions with the NIHR HTA in December 2018, it was decided to terminate the study after 6 month follow-up data collection without reaching the planned recruitment target. Findings based on baseline data and 6-month follow-up will still be relevant for meta-analysis in this research area and to guide wider research in the field with regard to feasibility, study design, implementation and challenges faced in relapse prevention trials. In addition, data from the qualitative and EMA sub studies will lead to enhanced knowledge surrounding relapse prevention and strategies used. Data collection for 6-month follow-up is expected to be complete by June/July 2019. The first draft of the statistical analysis plan (SAP) was drafted in January 2019.

This SAP was written once the decision to shut down the study (December 2018) was made as original endpoints and analyses planned in the study protocol, no longer apply. Indeed, no 12-month follow-up data will be collected. The present SAP is a revised plan for the curtailed trial based on the information in the study protocol V4.1 which was finalised on 8 August 2018. The trial statistician has not seen any trial data apart from recruitment updates and has remained blinded throughout the SAP revision.

Amendments to the objectives, aims and analyses are also necessary as the trial did not reach its expected target sample size (N = 1400), in which the trial was powered for. In total, 235 participants were randomised (105 in the UK and 130 in Australia).

Primary Objective

Original

To determine if providing additional strategies designed to help people cope with temptations to smoke (online Structured Planning and Prompting Protocol [S3P] and/or access to smoking replacement [SR] products) when provided following the successful completion of a smoking cessation programme (i.e. at around 4 weeks post quit), reduce relapse rates at 12 months post quit date.

Curtailed Trial

To determine if providing additional strategies (the number of interventions: 0 (UC) vs. 1 (SR or S3P) vs 2 (SR+S3P)) designed to help people cope with temptations to smoke when provided following the successful completion of a smoking cessation programme, reduce relapse rates at 6 months post quit date. See page 13 for full details.

Secondary Objectives

Original

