4. How feasible and acceptable are the strategies to participants, and what are the barriers and facilitators to sustained cessation during the trial period? How are the relapse prevention strategies used, and are patterns of use related to cessation outcomes? (Explorative analyses of EMA/qualitative sub study data complementing cessation reports at follow-ups; quantitative analysis will not be possible in the curtailed trial.)
5. What are the rates of negative aspects (adverse events) reported in people who use a smoking replacement product compared to those who do not and does this vary by type of product used?

Primary Outcome

Original

Sustained abstinence between 1 and 12 months post quit date, with no reported relapse (7 or more days of continuous smoking) and no smoking at all in the last month, biochemically verified.

Curtailed Trial

Sustained abstinence (i.e. no relapse) between 1 and 6 months post quit date. Relapse is defined as 7 or more days of continuous smoking reported at any follow up or any cigarettes smoked (even just a puff) in the last month at 6 months. Abstinence will be based on self-report as no biochemical validation was planned at 3- or 6-month follow-up.

Original Secondary Outcome

1a. Sustained abstinence using different criteria for the primary outcome (e.g. 6 months sustained abstinence according to Russel Standard definition) and different assumptions about missing cases.

1b. Point prevalence abstinence at 3 and 6 months and shorter-term period prevalence outcomes

1c. Sustained reduction in cigarette consumption of at least 50% from baseline in those who do not achieve abstinence at 6 months.

2. Evaluations of likely mechanisms of effect in particular focusing on these strategies that were encouraged and participant perceptions of effect (e.g. participant ratings), including use of EMA/qualitative sub studies

3. Dose response effects - is the dose of the interventions, or extent of compliance, associated with relapse

4. Effects of intervention components (e.g. on relapse rates, participant ratings etc.) by country and on people from different socioeconomic and ethnic groups, of different gender, with different prior smoking habits, and those who stopped smoking using different forms of medication

5. Cost-effectiveness of the different strategies

Curtailed Trial Secondary Outcome

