- Users of the SSS in the UK and the Quitline in Australia who are abstinent in the last 2 weeks of treatment (treatment period is typically 4 weeks post QD) and are still abstinent at point of recruitment. Additionally, in Australia, ethics permission was secured to recruit those quit between 7 and 100 days, and recruit from two additional sources: social media (via Facebook advertising) and St Vincent's Hospital, Melbourne.
- Willing to use a smoking replacement product or online behavioural support tool if allocated to use
- Aged 18 years and older
- Own a mobile phone
- Has Internet access
- Able to read/write/understand English

Exclusion Criteria

[figure not shown]
- Enrolled in other smoking cessation/relapse prevention research
- Currently using EC/oral NRT and planning to use for longer than 3 months

Study Design

[figure not shown]
This is a factorial randomised controlled trial with two comparisons added to usual care (UC; UC is generally 8-12 weeks of pharmacotherapy (e.g. varenicline or NRT), plus standard counselling provided from the commencement of the quit attempt), augmented by a series of text messages available in all conditions. Participants will be individually randomised to one of four arms: UC (Usual Care), SR (Smoking Replacement), S3P (Structured Planning and Prompting Protocol), or SR plus S3P.

Study Scheme Diagram

The study scheme below outlines the flow of participants through the trial and key time points for the original trial and curtailed trial.

Curtailed trial

Randomisation Procedures

Participants were randomised (stratified by country in permuted blocks of random size) to one of four study arms described in the Schedule of Intervention below. The randomisation ratio was 1:1:1:1 across the 4 study arms. Randomisation was done automatically via Stata code with the results imported into the web based program (Quest Engage) that directed the baseline study questionnaire, and occurred after all key baseline information was collected. The 4 arms are described as follows:

- 1. UC arm (control group, receives neither intervention):** If used as part of UC, this group will be encouraged to continue use of base medication (e.g. varenicline or patch) until the end of the recommended period of use.

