They will be offered a version of the text messaging program without the specific strategies focused on in the S3P intervention. They will not be provided with any SR products (although they may be using them as part of their continued UC at the SSS).
- 2. Only SR:** This group will be offered a SR product. Participants will choose one SR product from up to three NRT and EC options (two fast acting NRT and one EC) to use as a coping strategy if at risk of relapse.
- 3. S3P / No SR arm:** After answering some additional questions participants will receive an initial personalised, tailored plan, focusing on S3P (Structured Planning and Prompting Protocol) strategies, and access to a tool designed to help them form implementation intentions for situational temptations to smoke (Problem Planner). These will be reinforced with additional text messages that will remind them to rehearse these self-statements, replacing and extending the more general messages used in the UC condition. These resources will be available to them on the internet for future use, with prompts to use when recommended (around the time of stopping base medication or when having additional problems).
- 4. S3P plus SR arm:** Participants will receive both interventions, with S3P modified to include integrated references to SR as a relapse prevention strategy.

Curtailed Trial Follow-up (no 12-month follow-up)

Participants will complete online questionnaires at 3 and 6 months post-QD (approximately 2- and 5-month post-recruitment) for smoking status and other measures. Participants will be contacted by telephone to complete the questionnaires if they prefer, or if they do not respond to the email prompts to complete them. Participants will receive £10 (UK)/\$20 (Australia) for completing the questionnaires at 3 and 6 months.

Although the research team had telephone contact with some participants at 3 and 6 months to assess outcomes no counselling was provided at these follow-up calls.

NB. Participants who did not want to use a nicotine based product were not randomised into the study, but were offered access to the S3P program, and were followed up passively only (i.e. they received email reminders to complete the follow up questionnaires online, but were not actively followed up by the study team). The analysis of this subsidiary study is not included in this SAP.

Curtailed Measures

Baseline:

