All analyses will be conducted using a logistic regression where relapse status is regressed onto an ordinal predictor which codes the number of active interventions assigned (0, 1, or 2) adjusted for the stratified (i.e. country). A likelihood ratio test will be conducted initially to assess whether the ordinal predictor should be modelled as continuous or categorical. If the treatment effect is positive, we will also explore the moderating role of country on the treatment effect by including an interaction term between 'treatment' and country. Estimates and 95% confidence intervals will be presented.

Sensitivity analyses of the primary outcome

To assess the robustness of the results, a series of sensitivity analyses will be conducted using different approaches to impute missing information; specifically, we will use multiple imputation by chained equation [26] and complete case analysis where we exclude cases with missing outcomes. To build the multiple imputation model, we will explore differences in baseline measures between participants with complete and missing outcome measures.

Sensitivity analyses will also explore alternative definition of sustained abstinence for the primary outcome, e.g. Russel standard defined as not smoking more than 5 cigarettes since 2-weeks post quit.

Lastly, per protocol analysis will also be conducted to exclude those participants who were not using their allocated product. This will allow us to assess the robustness of the results following departures from the randomised treatment.

No statistical testing (p -value) will be reported for the sensitivity analyses as we are mostly interested in assessing how robust the results are.

All analyses will be carried out in Stata.

Number needed to treat

The number needed to treat (95%CI) for one additional person not to relapse will also be estimated.

Adverse events

The number of adverse events and serious adverse events by study arm will be presented and specific events will be listed.

Tables to be included

- Descriptive statistics of baseline characteristics by study arm.
- Proportion of missing information on the primary and secondary outcomes by study arm.

- Differences in baseline characteristics between patients with complete vs. missing information on the primary outcome.

Figures to be included

- CONSORT diagram

References

1. Ferguson, J., et al., *The English smoking treatment services: one-year outcomes*. *Addiction*, 2005. **100**(s2): p. 59-69.

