Sustained abstinence (i.e. no relapse) between 1 and 6 months post quit date. Relapse is defined as 7 or more days of continuous smoking reported at any follow up or any cigarettes smoked (even just a puff) in the last month at 6 months.	
6 month survey:
 
Have you smoked at all since we last surveyed you on <inset date>?
 
 1. No, not even a puff 2. Yes – just a few puffs 3. Yes – 1- 5 cigarettes in total 4. Yes – more than 5 cigarettes in total 
When did you last smoke a cigarette?
 
 1. Today 2. Yesterday 3. 2-6 days ago 4. 1-2 weeks ago 5. More than 2 weeks to 30 days (1 month) ago 6. More than 1 month ago 
3 and 6 month survey:
 
At any time since <last survey> did you smoke every day for a week or more?
 
 1. Yes 2. No

Secondary outcomes

Outcome and definition	Data source
Sensitivity analyses using different approaches to imputed missing smoking status at 6 months;	
6 month survey:
 
Have you smoked at all since we last surveyed you on <inset date>?
 
 1. No, not even a puff 2. Yes – just a few puffs

specifically, multiple imputation by chained equation.
	
 3. Yes – 1- 5 cigarettes in total 4. Yes – more than 5 cigarettes in total 
When did you last smoke a cigarette?
 
 1. Today 2. Yesterday 3. 2-6 days ago 4. 1-2 weeks ago 5. More than 2 weeks to 30 days (1 month) ago 6. More than 1 month ago 
3 and 6 month survey:
 
At any time since <last survey> did you smoke every day for a week or more?
 
 1. Yes 2. No

Point prevalence abstinence at 3 months, defined as no smoking (not even a puff) in the past seven days
	
3 month survey:
 
Have you smoked at all since we last surveyed you on <inset date>?
 
 1. No, not even a puff 2. Yes – just a few puffs 3. Yes – 1- 5 cigarettes in total 4. Yes – more than 5 cigarettes in total 
3 month survey:
 
When did you last smoke a cigarette?
 
 1. Today 2. Yesterday 3. 2-6 days ago 4. 1-2 weeks ago 5. More than 2 weeks to 30 days (1 month) ago 6. More than 1 month ago

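### For Australians enrolled well before or after four weeks, the stated 1-to-6-month outcome window does not match the survey items it is derived from, and time since quitting is left out of the model

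*SAP*

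**What the plan says.** Under Inclusion Criteria, the SAP describes recruits coming from a cessation service whose "treatment period is typically 4 weeks post QD". It then adds that in Australia "ethics permission was secured to recruit those quit between 7 and 100 days", and that social media and one hospital were further sources there. Early termination and curtailed trial gives the sample: "In total, 235 participants were randomised (105 in the UK and 130 in Australia".

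For everyone alike, the curtailed primary outcome is "Sustained abstinence (i.e. no relapse) between 1 and 6 months post quit date". Relapse means at least seven consecutive days of smoking reported at a follow-up, or any smoking in the last month at six months. Curtailed Trial Follow-up places the surveys "at 3 and 6 months post-QD (approximately 2- and 5-month post-recruitment".

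Appendix 1 builds the primary outcome from the 3- and 6-month surveys only. The item for the seven-day criterion is "At any time since <last survey> did you smoke every day for a week or more". Under Analysis of primary and secondary outcomes, the logistic model is "adjusted for the stratified (i.e. country"; no other covariate is named. Country is also the only stratification factor (Randomisation Procedures).

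**The concern.** The outcome window and the two ways of dating the surveys agree only for someone who enrols about one month after quitting. The Australian window runs from one week to more than three months. The SAP has no rule for a person randomised before the outcome window opens, well inside it, or after the 3-month survey date.

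Three things follow. The label of the primary outcome does not describe what the survey items can record for such a person. Time at risk after randomisation differs widely within Australia, and a country term cannot absorb a spread within one country. The 3-month point-prevalence outcome has no meaning for someone enrolled after three months. The SAP says that the trial's remaining value lies largely in meta-analysis, and a reader extracting its results needs to know over what interval relapse was counted.

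**Working it through.** **Inputs.** Enrolment days 7 to 100 and about 28 (Inclusion Criteria); outcome window of 1 to 6 months post quit (Primary Outcome); surveys at 3 and 6 months post quit, or about 2 and 5 months after recruitment (Curtailed Trial Follow-up); 235 = 105 + 130 randomised. One month = 365.25/12 = 30.4 days, so 3 months is day 91.3, 6 months is day 182.6, and the 1-to-6-month window lasts 5 × 30.4 = 152.2 days.

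**The SAP's own timing, reproduced.** For enrolment on day 28, the surveys fall 91.3 − 28 = 63.3 days (2.1 months) and 182.6 − 28 = 154.6 days (5.1 months) after recruitment. The stated 2 and 5 months are right for that person.

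**The same sums for other enrolment days.**

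| Enrolled on day | Enrolment to 3-month survey (days) | Enrolment to 6-month survey | Outcome window before randomisation | Months post quit if surveys fall 2 and 5 months after recruitment |
|---|---|---|---|---|
| 7 | 84.3 | 175.6 days (5.8 months) | 0 | 2.2 and 5.2 |
| 28 | 63.3 | 154.6 days (5.1 months) | 0 | 2.9 and 5.9 |
| 60 | 31.3 | 122.6 days (4.0 months) | 29.6 days (19%) | 4.0 and 7.0 |
| 100 | −8.7 | 82.6 days (2.7 months) | 69.6 days (46%) | 5.3 and 8.3 |

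- *Enrolled day 100.* The 3-month survey date is 8.7 days before enrolment. Of the outcome window, 100 − 30.4 = 69.6 days precede randomisation, and 69.6/152.2 = 46%. The items listed for the primary outcome do not cover that stretch.
- *Enrolled day 7.* There are 30.4 − 7 = 23.4 days after randomisation but before the window opens. A week of daily smoking then lies outside the stated window, but the 3-month item counts it.
- *Spread.* 175.6/82.6 = 2.1, so time from randomisation to six months post quit varies about two-fold.
- *Anchor.* If surveys were dated from recruitment instead, the six-month outcome of a day-100 enrolee would be read at 8.3 months post quit. The two descriptions of survey timing then differ by more than two months.

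**How many.** 130/235 = 55.3% is the whole Australian sample, and so an upper bound. The SAP gives no distribution of enrolment days.

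**What the covariate is worth.** The SAP's 78% power for the 0/1/2 analysis (one-sided 0.05) reproduces. Take n = 58.75, 117.5 and 58.75, relapse 0.70, 0.58 and 0.48, and centred scores −1, 0 and 1.
- T = 58.75 × (0.48 − 0.70) = −12.93.
- Pooled rate = (0.70 + 2 × 0.58 + 0.48)/4 = 0.585.
- Null variance = 0.585 × 0.415 × 117.5 = 28.53.
- Alternative variance = 58.75 × (0.70 × 0.30 + 0.48 × 0.52) = 27.00.
- Power = Φ[(12.93 − 1.645 × √28.53)/√27.00] = Φ(0.80) = 78.7%.

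The SAP gives no relapse rate by time since quitting, so any gain rests on assumed gradients. In 3,000 simulated trials per scenario, with control relapse in Australia falling between day 7 and day 100, one-sided power without and with the covariate was:
- 80% falling to 45%: 0.767 and 0.774 (gain 0.7 points).
- 85% falling to 30%: 0.754 and 0.766 (gain 1.2 points).
- 90% falling to 30%: 0.735 and 0.767 (gain 3.2 points).

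**The case against.** The strongest reply is that the operative definition already limits itself. Seven-day relapse counts only if reported at a follow-up, so it is largely confined to smoking after randomisation whatever the label says. The last-month criterion is the same for everyone assessed at six months post quit. This stands: the fault is in the label and its fit to some participants, not in the whole endpoint.

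For late enrolees, the time before randomisation is not a blank. Recruits had to be abstinent at recruitment, and baseline items ask about smoking since the quit date. Where no 3-month survey exists, the six-month recall can run back to baseline. That is fair, although Appendix 1 lists those baseline items for the Russell Standard outcome and not for the primary one.

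For early enrolees, misclassification needs an unusual course: a week of daily smoking before day 30, then recovery, then no further relapse and a clean last month. Anyone who kept smoking is a relapse on either reading. This too stands.

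Survey windows may also be set out in the protocol or in the study scheme, neither of which is visible here, so the absence of a visit-window rule is weak evidence by itself. The point rests on statements within the SAP that do not fit one another.

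A reader might infer more than the document supports:
- *That 55% of the sample is affected.* Australians enrolled near four weeks fit the schedule, and the survey is impossible only after about day 91.
- *That the arm comparison is biased.* Randomisation was stratified by country, so time since quitting is balanced across arms in expectation. What remains is chance imbalance and some lost precision.
- *That the missing covariate costs much power.* Even steep assumed gradients give at most about 3 points.
- *That counting from randomisation equalises time at risk.* It does not; the range of 83 to 176 days remains.

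**Conclusion.** The point holds as one of definition and of a modest, nearly free improvement. For some Australian participants, at most 130 of 235 and in unknown number, the stated window does not match the derivation. Their follow-up from randomisation ranges from about 83 to 176 days, and those enrolled after about day 91 have no 3-month post-quit assessment. The calendar results rest only on the SAP's own dates and a 30.4-day month. The gain of about 0 to 3 power points rests on assumed relapse gradients. That time since quitting is prognostic is plausible but is not shown in the SAP. The validity of the randomised comparison and the reproduced 78% power are not in question.

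**What to change.** 1. State the primary outcome as no relapse reported from randomisation to six months post quit date, keeping the last-month criterion at six months. Say that surveys are dated from the quit date, and that the recruitment-based equivalents apply only to enrolment near one month.
2. Add days from quit date to randomisation as a pre-specified covariate in the primary logistic model, beside country, and in the multiple imputation model. At present imputation variables are to be chosen by exploring baseline differences, so this one may or may not enter. The covariate also takes up differences in relapse risk that go with unequal time at risk, though it does not make that time equal.
3. Exclude participants enrolled after about day 91 from the 3-month point-prevalence analysis, and do not count them as missing or as smoking. The SAP's missing-as-smoking rule names six months only, so their status is now undefined. Enrolment day is fixed before randomisation, so the exclusion keeps the arms comparable.

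A sensitivity analysis limited to enrolment near four weeks is optional. It needs numeric bounds set in advance, because the SAP gives only a typical value, and it would reduce an already small sample.

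The cost is a few sentences and one model term. No new data are needed: quit date must be known because follow-up is scheduled from it. The SAP was revised after the decision to close the trial, by a statistician who had seen only recruitment updates, so these choices could be fixed without knowledge of outcomes.

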Modern information technology, in particular web-based resources and text messaging, offers a new and more convenient way of maintaining contact with clients to provide ongoing support. Recent data show that an online Structured Planning and Prompting Protocol (S3P) reduced relapse rates between 1-24 weeks from 71% to 61% [17]. The S3P is designed to focus planning on strategies to deal with temptations to smoke. The core element is using a method of "If in a particular situation, then do some specific set of actions to prevent relapse". This form of self-statement has been shown in experimental work to improve the cuing of the desired action in the context of the situation occurring where it is likely to be needed [18]. This approach can be delivered online and can be enhanced by mobile phone text messages. Digital technology promises a new approach to extending supportive contact. Texting interventions are inexpensive and can be easily

disseminated on a large scale. We have piloted the use of ongoing text-based contact to prevent relapse in 202 SSS clients, who were abstinent 4-weeks after their quit date [11]. Clients received 17 personalised messages, 9 that were interactive, which were sent weekly for 12 weeks and fortnightly for 6 months. Unlike invitations to attend sessions or call their advisors, the texting intervention was well received by recent ex-smokers (70% gave an overall score for helpfulness of the messages of 4 or 5 on a 5-point scale) and the retention rates were much better than with face-to-face or reactive telephone-based approaches.

The proposed trial would be the first randomised study of these interventions for relapse prevention, and thus will generate new knowledge. The intervention itself would build directly on previous UK and Australian work while the trial would use methods validated extensively in previous research.

Early termination and curtailed trial

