Curtailed Trial Sample Size

The analysis plan is for the curtailed trial. The study was originally powered to be able to assess the effectiveness of the SR and S3P interventions (main effects); SR (2 arms) vs. no SR (2 arms) & S3P (2 arms) vs. no S3P with power = .90 and $\alpha = 0.025$.

With a final sample size of 235 and using $\alpha 0.025$, we have 30% power to detect a difference between arms (i.e. S3P vs no S3P or SR vs no SR), if one really exists. If we wanted to compare the 4 arms simultaneously in 1 model, the analysis would have 51% power with $\alpha 0.05$ (one-sided).

An alternative approach is to consider the study arms as an ordinal measure where participants are allocated to 0 (UC), 1 (S3P or SR arm), or 2 interventions (S3P+SR). We can assess whether the number of interventions received affects continued abstinence. With a final sample size of 235 and $\alpha = 0.05$ one-sided we have 78% power and this would also avoid multiple testing. We expect the intervention to be more effective at 12 months and, therefore, this is an optimistic power estimate but we can't estimate to what degree.

Overall, the latter approach offers us a viable option to explore differences in therapy on smoking relapse. The revised analyses for the curtailed trial will be useful for future meta-analysis looking at the impact of smoking replacement and/or Structured Planning and Prompting Protocol (S3P) on relapse.

ANALYSIS PLAN

Descriptive statistics

Participants' characteristics at baseline and follow-up will be presented broken down by all 4 arms using appropriate descriptive statistics; mean and standard deviation for continuous measures that are approximately symmetric; median and quartiles if they are skewed distributions. Discrete outcomes should be described using both the number and proportion (percentage). Similarly, summary measures of the primary (i.e. quit rates) and secondary outcomes by arms will also be presented.

Analysis of primary and secondary outcomes

Analyses for the primary and secondary outcomes will use the intention-to-treat (ITT) approach. All participants will be included in the analysis and will be analysed according to the treatment group to which they were randomised. All participants with missing outcomes at six months will be considered to be smoking (relapsed) as per Russell Standard, and to have not reduced their number of cigarettes smoked per day from baseline.

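### The power figures behind the ordinal primary analysis use three different error rates, and the 78% (one-sided 0.05) does not match the planned 95% confidence intervals, for which power is about 68%

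*SAP*

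**What the plan says.** The SAP section Curtailed Trial Sample Size compares three analyses for the 235 randomised participants.

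- **Main effects** (SR vs no SR, S3P vs no S3P), α = 0.025, sidedness not stated: "we have 30% power to detect a difference between arms".
- **Four arms in one model**: "the analysis would have 51% power with" α = 0.05, labelled one-sided.
- **Number of interventions as an ordinal predictor**, α = 0.05: "one-sided we have 78% power and this would also avoid multiple testing".

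It adds that effects are expected to be larger at 12 months and "therefore, this is an optimistic power estimate", by an amount it says cannot be estimated. It then concludes that the ordinal approach is the viable one. The only planning rates are under Original Sample Size: relapse by 12 months of 70% in usual care, 58% with one intervention and 48% with both. The curtailed primary outcome is at 6 months.

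Under Analysis of primary and secondary outcomes, the model is a logistic regression on the number of interventions, adjusted for country. No significance level or sidedness is given, only that "Estimates and 95% confidence intervals will be presented". The number needed to treat is also to be given with a 95% interval.

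**The concern.** The power figures are the stated reason for replacing the factorial main effects with the ordinal test, so they should be comparable and should describe the inference that will be reported. They do neither. A reader who compares 30% with 78% is comparing a two-sided 0.025 test with a one-sided 0.05 test. A reader who expects 78% power and then reads a 95% interval is looking at a stricter criterion than the one the power refers to.

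At stake is the reading of a borderline primary result. With no test level in the analysis section, a one-sided p below 0.05 and a 95% interval that includes no effect could both be reported, and the plan does not say which governs. Country moderation is to be explored only if the treatment effect is positive, and the SAP does not say whether that means significant or merely in the favourable direction.

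**Working it through.** **Inputs.** N = 235 (Early termination and curtailed trial). Allocation is 1:1:1:1 (Randomisation Procedures), so 58.75 / 117.5 / 58.75 participants have 0 / 1 / 2 interventions. Relapse is 0.70 / 0.58 / 0.48 (Original Sample Size). Missing outcomes count as relapse, so nothing is deducted for dropout. The mean rate is (0.70 + 2×0.58 + 0.48)/4 = 0.585, with null variance 0.585×0.415 = 0.2428.

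**Ordinal test (trend, scores 0, 1, 2).**
- Numerator: 58.75×(0.70 − 0.48) = 12.925.
- Null SD: √(0.2428×117.5) = 5.341.
- SD under the alternative: √(58.75×(0.70×0.30 + 0.48×0.52)) = 5.196.
- Power = Φ((12.925 − z×5.341)/5.196).
- One-sided 0.05 (z = 1.645): Φ(0.80) = 78.7%, which reproduces the stated 78%.
- Two-sided 0.05 (z = 1.960): Φ(0.47) = 68.2%.
- Two-sided 0.025 (z = 2.241): Φ(0.18) = 57.3%.

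In 10,000 simulated trials with the country-adjusted logistic model, power was 79.3%, 68.1% and 56.8%.

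**Main effect.** The margins are (0.70 + 0.58)/2 = 0.64 and (0.58 + 0.48)/2 = 0.53, with 117.5 per side.
- Null SE: √(2×0.2428/117.5) = 0.0643.
- Alternative SE: √((0.64×0.36 + 0.53×0.47)/117.5) = 0.0639.
- Power = Φ((0.11 − z×0.0643)/0.0639).
- Two-sided 0.025 gives 29.7%, which reproduces the 30%. One-sided 0.025 would give 40.1%, so the 30% is two-sided. The original 257 per arm also reproduces at two-sided 0.025 (with continuity correction).

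**Four arms.** Noncentrality = 58.75×(0.115² + 2×0.005² + 0.105²)/0.2428 = 5.88 on 3 df. At 0.05 the power is 50.9%, which reproduces the 51%. A 3-df comparison has no direction. Doubling the level to 0.10, as a stand-in for one-sided 0.05, would give 63%.

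**Like for like (12-month rates).**

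| | two-sided 0.025 | two-sided 0.05 | one-sided 0.05 |
|---|---|---|---|
| Main effect | 29.7% | 40.1% | 52.7% |
| Ordinal | 57.3% | 68.2% | 78.7% |

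**Where the gap comes from.** The unrounded gap is 78.7 − 29.7 = 49.0 points. Taken in this order: ordinal coding 57.3 − 29.7 = 27.6; one test at 0.05 instead of two at 0.025, 68.2 − 57.3 = 10.9; one-sidedness 78.7 − 68.2 = 10.5.

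**Discordance.** At the planned effect, the share of trials with one-sided p<0.05 and a 95% interval that includes no effect is 78.7 − 68.2 = 10.5 points (79.3 − 68.1 = 11.2 in the simulation).

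**6-month illustration only.** The background text cites an earlier S3P study that "reduced relapse rates between 1-24 weeks from 71% to 61" per cent. Suppose SR had the same effect. A combined-arm rate of 51% (additive) then gives two-sided power of 60.6%. A rate of 0.61²/0.71 = 52.4% (multiplicative) gives 54.4%. Combining on the odds scale (50.0%) gives 64.9%.

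**The case against.** The strongest reply is that no arithmetic is wrong. Every figure reproduces, the SAP prints the sidedness in the same sentence as the 78%, and the next sentence calls the figure optimistic. All of that stands, so a reader should not infer that the 78% is miscalculated or that its main caveats were concealed.

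Second, part of the change in alpha is legitimate. Two main-effect tests at 0.025 give way to one test at 0.05, and the SAP names the avoidance of multiple testing as an advantage. It is tempting to say that about half of the gain is merely a relaxed error rate. That overstates it: about 11 of the 49 points are the price of multiplicity, and only 10 to 11 are one-sidedness.

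Third, a directional objective can support a one-sided power calculation, and 95% intervals suit a trial meant to feed meta-analysis. That is fair, but it does not settle which criterion governs the primary test, because the analysis section states none.

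Fourth, it is tempting to give power at 6 months as 54% to 68%. The documents do not support that range. The 68% still uses 12-month rates. The 54% borrows an S3P-only result and needs an assumed SR effect and an assumed combined-arm rate. It also places 71% control relapse at 24 weeks in a trial that expects 70% by 12 months. Nor is 54% a floor: two-sided power is 45% at three quarters of the planned effect and 24% at half. The SAP's statement that it cannot size the optimism is defensible.

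**Conclusion.** The point holds as a mismatch of error rates, not as an arithmetic error. The 30%, 51% and 78% rest on two-sided 0.025, a non-directional 0.05 and one-sided 0.05 respectively, and the label on the 51% is wrong. The reported 95% intervals correspond to two-sided 0.05, where ordinal power is about 68%, roughly 10 points below the stated figure.

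This rests on the 12-month rates, equal arms and the ordinal predictor being kept linear. If effects at 6 months are smaller, as the SAP expects, power is lower by an amount the documents do not fix.

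A reader might infer that the ordinal analysis was chosen on a false basis. It was not: it leads by 26 to 28 points at every common alpha (40% vs 68% at two-sided 0.05). The sample was already fixed at 235, so no model or estimate changes. What changes is the stated power and the clarity of the decision rule.

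**What to change.** 1. In the analysis section, state one alpha and sidedness for the primary test and match the interval to it: two-sided 0.05 with a 95% interval, or one-sided 0.05 with a 90% interval.
2. If two-sided, restate ordinal power as 68% under the 12-month rates.
3. Show the options on a common basis. At an overall two-sided 0.05 they are 30% per main effect (two tests at 0.025), 51% for four arms and 68% for the ordinal test.
4. Delete the one-sided label from the 51%.
5. If a 6-month power is given, present it as an illustration with its assumptions. An example is 54% to 61% two-sided, if SR shares the cited S3P effect and the combined arm relapses at 51% to 52%. It should not appear as a planned figure.

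The cost is a few sentences of SAP wording, best settled while the statistician is still blinded, and a less favourable stated power.
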